### **6.3.1. Unscheduled Termination from the Study**

Withdrawal of consent: Subjects or parents/guardians who request to discontinue study treatment will remain in the study and must continue to be followed for protocol specified follow-up procedures. The only exception to this is when a subject or parents/guardians specifically withdraws consent for any further contact with him or her or persons previously authorized by the subject or parents/guardians to provide this information. Subjects or parents/guardians should notify the investigator in writing of the decision to withdraw consent from future follow-up, whenever possible.

The withdrawal of consent should be explained in detail in the medical records by the investigator, as to whether the withdrawal is only from further receipt of investigational product or also from study procedures and/or post-treatment study follow-up, and entered on the appropriate CRF page. In the event that vital status (whether the subject is alive or dead) is being measured, publicly available information should be used to determine vital status only as appropriately directed in accordance with local law.

Lost to follow-up: All reasonable efforts must be made to locate subjects to determine and report their ongoing status.

This includes follow-up with persons authorized by the subject or parents/guardians as noted above. Lost to follow-up is defined by the inability to reach the subject after a minimum of 2 documented phone calls, faxes, or e-mails as well as lack of response by the subject or parents/guardians to 1 registered mail letter. All attempts should be documented in the subject's medical records. If it is determined that the subject has died, the site will use permissible local methods to obtain the date and cause of death. If the investigator's use of a third-party representative to assist in the follow-up portion of the study has been included in the subject's informed consent, then the investigator may use a sponsor-retained third-party representative to assist site staff with obtaining the subject's contact information or other public vital status data necessary to complete the follow-up portion of the study. The site staff and representative will consult publicly available sources, such as public health registries and databases, in order to obtain updated contact information. If, after all attempts, the subject remains lost to follow-up, then the last-known-alive date as determined by the investigator should be reported and documented in the subject's medical records.

Subjects may withdraw from the study at any time at their own request, or they may be withdrawn at any time at the discretion of the investigator or sponsor for safety or behavioral reasons, or the inability of the subject to comply with the protocol-required schedule of study visits or procedures at a given study site.

If a subject does not return for a scheduled visit, every effort should be made to contact the subject. All attempts to contact the subject or parents/guardians and information received during contact attempts must be documented in the subject's medical record. In any circumstance, every effort should be made to document subject outcome, if possible. The investigator should inquire about the reason for withdrawal, request that the subject return all unused investigational product(s), request that the subject return for a final visit, if applicable, and follow up with the subject regarding any unresolved adverse events (AEs).

If the subject withdraws from the study, and also withdraws consent for disclosure of future information, no further evaluations should be performed, and no additional data should be collected. The sponsor may retain and continue to use any data collected before such withdrawal of consent.

### **6.3.1.1. Subject Removal from the Study**

When subjects are removed from the study the following information will be obtained:

- a. The date of the last administration and dose of study medication and all observations collected up to the time of termination will be recorded on the subject's CRF along with the reason for termination.
- b. An examination of the subject will be conducted, if possible. All assessments that would be conducted at Visit 7 (EOS) should be performed.

### **6.3.2. Subject Replacement Policy**

All subjects who prematurely discontinue from the study and do not complete the PD Phase will be replaced until 50 subjects have viable PD Phase Anti-Xa data.

## **7. TREATMENTS**

Dalteparin sodium (Fragmin®) will be provided in:

- Multiple dose vials of 25,000 IU/1 mL (3.8mL for US or 4mL for ROW) containing preservative benzyl alcohol;
- Preservative-free single dose vials of 2,500 IU/1 mL (4mL) [where available];
- Preservative-free 10,000 IU / 1 mL single-dose graduated syringe (can be diluted as needed per the IP Manual).

Dosing administration is subcutaneous, twice daily. Study medication can only be administered to patient by a healthcare professional (ie, study nurse) or trained parent/caregiver. Hospital nurses that may administer study medication to in-patient subjects do not require GCP training. However, they must receive study medication administration training from the site staff and the training should be documented.

The use of cannulas to administer study medication is not permitted.

Subjects, aged 0 to less than 8 weeks will receive twice daily dose of 125 IU/kg. Subjects, aged greater than or equal to 8 weeks to less than 2 years will receive twice daily dose of 150 IU/kg. Subjects aged greater than or equal to 2 years to less than 8 years and subjects aged greater than and equal to 8 years to less than 12 years will receive twice daily dose of 125 IU/kg. Subjects aged 12 years to less than 19 years will receive twice daily dose of 100 IU/kg.

All subjects will have dose adjustments in 25 IU/kg increments or decrements based upon Anti-Xa therapeutic goal range of 0.5 to 1.0 IU/mL. Dalteparin sodium will be administered subcutaneously every 12 hours  $\pm$ 1 hour (no less than 8 hours between doses). However, if a dose is not able to be delivered every 12 hours  $\pm$ 1 hour, administer the dose (no less than 8 hours between doses) and record the actual dosing time.

- Dose Adjustment Phase (Baseline/Day 1 up to Day 7):

Anti-Xa levels will be measured at 4 hours post-dose ( $\pm 1$  hour) daily for up to 7 days to determine if the anti-Xa level is within the target therapeutic range of 0.5 to 1.0 IU/mL.

However, the first Anti-Xa level may be taken after the first, second or third dose per Investigator judgment. The next dalteparin dose will be adjusted if the target therapeutic range is not achieved. If the therapeutic range is not achieved, the dalteparin dose must be adjusted per protocol. All plasma samples should be drawn within the assigned window at each visit, however, if this is not possible, record the actual time the sample is drawn). Plasma samples drawn during the Dose-Adjustment Phase and Follow-Up Phase that deviate outside the  $4 \pm 1$  hr window cannot use the anti-Xa reference range, 0.5-1.0 IU/mL, and should be repeated the next day for both central and local labs. The actual dosing time prior to the repeat plasma sample draw and the actual time of the repeat sample draw must be recorded.

After dose adjustment, Anti-Xa levels should be re-measured after the first, second or third dose per Investigator judgment. Dosage can be adjusted a maximum of up to 6 times (up to Day 7) to achieve Anti-Xa therapeutic range. If the target range is not achieved within the 7 day period, the subject is withdrawn from the study.

The dose at which a therapeutic Anti-Xa level is achieved is then maintained as the therapeutic dose in subsequent phases of the study unless dose adjustment is necessary.

- Pharmacodynamic Phase (Following completion of Dose Adjustment Phase) Day 2 or 3 up to Day 14 [up to 7 days]: Subjects completing the Dose Adjustment Phase will enter into the PD Phase and continue daily dosing every 12 hours  $\pm 1$  hour of dalteparin sodium with the final maintenance therapeutic dose from the Dose Adjustment Phase (no less than 8 hours between doses). However, if a dose is not able to be delivered every 12 hours  $\pm 1$  hour, administer the dose (no less than 8 hours between doses) and record the actual dosing time. The plasma sample should be re-drawn, if possible, at the correct time point.
- Follow-up Phase (Visits 5, 6 and 7, following completion of Pharmacodynamic Phase): Dalteparin sodium will be administered subcutaneously every 12 hours  $\pm 1$  hour (no less than 8 hours between doses) during Visits 5, 6 and 7. However, if a dose is not able to be delivered every 12 hours  $\pm 1$  hour, administer the dose (no less than 8 hours between doses) and record the actual dosing time.
- No other systemic anticoagulants are allowed during the study with the exception of allowance of hospital specific Intra Venous (IV) (including central venous catheter line patency protocols which could include tissue Plasminogen Activator (tPA) and 3 IU/kg stat dose of unfractionated heparin, if the subject is unable to be treated with study drug due to an unanticipated hospital admission or a clinical event.

For non-cancer patients who stop dalteparin treatment prior to 3 months according to the ACCP Guidelines, Anti-Xa and Anti-IIa plasma sampling will not be required after study medication discontinuation. Treatment will be continued until any of the following occurs:

- New or progressive VTE (whether symptomatic or asymptomatic);
- Bleeding necessitating permanent discontinuation of anticoagulant therapy;
- Unexpected thrombocytopenia;
- Other AE necessitating discontinuation of study drug, withdrawal of consent or, scheduled study termination completion;
- Unexpected permanent discontinuation of anticoagulation therapy.

### 7.1. Dose Modification

In the event of medical procedures that may be required during the study, study medication can be held according to the institutional standard of care.

#### 7.1.1. Thrombocytopenia

Platelet count will be evaluated at Screening, Baseline, the last day of the dose adjustment and PD Phases, as well as the clinical visits during the Follow-up Phase. **For subjects whose platelet counts unexpectedly fall below 50,000/mm^3, HIT antibody testing will be performed. If the HIT antibody is positive, the subject must be discontinued.** If, during the study, the platelet count falls to below 50,000/mm^3 in a manner that is deemed to be expected by the treating oncologist (ie, consistent with chemotherapeutic effect on hematopoiesis), the administration of dalteparin should be temporarily stopped. After medical measures have been taken to increase the platelet count to a level  $\geq 50,000/\text{mm}^3$ , administration of dalteparin can be restarted. If the platelet count does not increase to a level of  $\geq 50,000/\text{mm}^3$  within 2 days in spite of medical measures, discontinuation of dalteparin should be considered.

Withdrawal of the subject from the study should be considered if platelet count does not increase to a level of  $\geq 50,000/\text{mm}^3$  after 5 days following discontinuation of dalteparin.

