## PROTOCOL FLOWCHART

**Table 1. Protocol Flowchart**

Assessments	Screen Visit 1	Baseline  Visit 2	Dose Adjustment Phase  Visit 3	PD  Visit 4	Follow-up Phase 			Unscheduled 		
					Telephone Contact 	Visit 5	Visit 6	Visit 7	Event	Visit
Day(s)- (Days may vary according to number of days required for Dose Adjustment Phase. Total treatment period is 90 days.)	-3 to -1	1	1 to 7	2/3 to 14	out-patient period	Days 15-44	Days 45-74	ET Days 75-104		
Informed Consent	x									
Medical History 	x	x								
Physical Exam 	x	x	x	x		x	x	x	x	x
Imaging	x	x						x 	x 	
Vital Signs	x	x	x	x		x	x	x	x	x
Clinical Laboratory:										
• Hematology/Coagulation	x 	x		x		x	x	x	x 	x 
• Antithrombin Activity	x 	x 	x	x		x	x	x	x 	x 
• Clinical Chemistries 	X	x		x		x	x	x	x 	x 
Pregnancy test, (serum or urine) if applicable	x	x	x	x		x	x	x	x	x
Evaluate Contraception if applicable	x	x	x	x	x	x	x	x	x	
Anti-Xa level 		L, C	L, C	C		L, C	L, C	L, C	L 	L 
Anti-IIa level 		C	C	C		C	C	C		
Dispense Study Drug 		x	x	x	x 	x	x		x	
Return Study Drug			x	x		x	x	x	x	x
Concomitant Medication	x	x	x	x	x	x	x	x	x	x
Adverse Events	x	x	x	x	x	x	x	x	x	x
Medication Compliance			x	x		x	x	x	x	x

Abbreviations: L- Local Lab, C- Central Lab

- Any change in medical history after the first dose of study medication is administered will be considered an AE.
- All subjects at high risk for bleeding or who have bleeding disorders such as Platelet Dysfunction, Protein Deficiency, DIC, Factor Deficiency, Hemophilia, ITP or Von Willebrand disease should not be considered candidates.

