### PD Phase:

Subjects completing the Dose Adjustment Phase will enter into the PD Phase. Dalteparin sodium will be administered subcutaneously every 12 hours  $\pm$  1 hour (no less than 8 hours between doses) with the maintenance therapeutic dose from the Dose Adjustment Phase.

However, if a dose is not able to be delivered every 12 hours  $\pm$ 1 hour, administer the dose (no less than 8 hours between doses) and record the actual dosing time. The PD Phase will last for 1 to 7 days in order to complete two PD samples for each subject (for the central lab, only). Subjects from each age group will be randomized according to a randomization scheme provided by the electronic system, IMPALA, into two different plasma sampling windows: 1 to 3 h and 5 to 8 h or 3 to 5 h and 8 to 12 h until at least 50 subjects provide viable PD Phase Anti-Xa values. All plasma samples should be drawn within the assigned window at each visit, however, if this is not possible, record the actual time the plasma sample is drawn in the Case Report Form (CRF) and repeat it when appropriate at the correct time, if possible.

The plasma sampling times can be spread over the duration of the PD Phase (up to 7 days) to avoid blood volume shifts if necessary. The assignment of the time points to the subjects within each age group will be centrally randomized.

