Plasma samples drawn during the Dose Adjustment Phase and Follow Up Phase that deviate outside the  $4 \pm 1$  hr window cannot use the Anti Xa reference range, 0.5 1.0 IU/mL, and should be repeated the next day. The actual dosing time prior to the repeat plasma sample draw and the actual time of the repeat sample draw must be.

In this study, the PD effect (Anti Xa level) is used as a surrogate (PK of dalteparin) for the time course of drug exposure because 1) analytical difficulty in measuring the dalteparin levels in plasma and 2) the instantaneous drug effect quantitated by Anti Xa level. Hence, the study is only characterizing the PD of dalteparin

The safety lab tests below will be conducted at the institutional local lab.

- Hematology/Coagulation: red blood cells (RBC), Hemoglobin, Hematocrit, Total White Blood Cell Count with differential, Platelet Count, PT, aPTT, International Normalized Ratio (INR);
- Antithrombin level at every visit that anti-Xa levels are drawn, and as per investigator's discretion at the Unscheduled Visit;
- Clinical Chemistry: Albumin, Alkaline Phosphatase, Alanine Aminotransferase (ALT), Aspartate Aminotransferase (AST), Calcium, Phosphorus, Total Protein, Magnesium, lactate dehydrogenase (LDH), Creatinine, Glucose, Total Bilirubin, Sodium, Potassium, Chloride, Carbon Dioxide, and Blood Urea Nitrogen (BUN), Creatinine Clearance:
- Pregnancy: Serum beta Human Chorionic Gonadotropin ( $\beta$  hCG) assessments or urine pregnancy tests will be performed for post-menarchal females at Screening or Baseline and all other study visits;
- Contact the sponsor if a subject is <1 month old.
- For any study sites that also require urine specimen collection in addition to blood draw for Creatinine Clearance reporting, according to local standards, urine collection will be conducted as required per local standards and Creatinine Clearance results will be provided in the CRF accordingly.

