### **9.3.2. Dose Adjustment Phase (Visit 3)**

If first dose adjustment is on conducted on Day 1, the first Dose Adjustment Phase Visit date would be the same as the Baseline Visit date. If first dose adjustment is conducted on Day 2, that would be the first Dose Adjustment Visit.

- (CRF pages to be completed when optimal dose is achieved)
- Physical Exam (at the end of the Dose Adjustment Phase);
- Vital Signs including weight and height (at the end of the Dose Adjustment Phase);
- Anti-Xa level (local and central laboratories) and Anti-IIa (central Lab only). Plasma samples drawn during the Dose-Adjustment Phase that deviate outside the 4 hour ( $\pm 1$  hour) window cannot not use the Anti-Xa reference range of 0.5-1.0 IU/mL and should be repeated the next day for both central and local laboratories;
- Antithrombin level (once at the end of the Dose Adjustment Phase);
- Serum or urine pregnancy tests (on post-menarche females) (only to be conducted once during the Dose Adjustment Phase, if there are multiple site visits during this phase);
- Dosing and administration compliance;
- Concomitant Medications/Treatments;
- AEs;
- Dispense Study Drug;
- Return Study Drug;
- Contraception check;
- Clinical lab for urine creatinine if applicable.

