### 9.3.3. Pharmacodynamic Phase

- (CRF pages to be completed when both of the two plasma samples have been drawn)
- Physical Exam (at the end of the PD Phase if it is >1 day);
- Vital Signs including weight and height (at the end of the PD Phase if it is >1 day);
- Clinical Laboratory (hematology/coagulation/clinical chemistry at the end of this phase);
- Serum or urine pregnancy tests (on post-menarche females);
- Anti-Xa level and Anti-IIa (central laboratory, only);
- Antithrombin level (once at the end of the PD Phase);
- Dosing and administration compliance;
- Concomitant Medications/Treatments;
- AEs;
- Dispense Study Drug
- Return Study Drug;
- Contraception check;
- Clinical lab for urine creatinine if applicable.

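### Section 7.1.1 asks for a platelet count at the end of the Dose Adjustment Phase, but Table 1 and Section 9.3.2 schedule none at Visit 3

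*Protocol*

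**What the plan says.** Section 7.1.1 of the protocol sets the platelet schedule: "Platelet count will be evaluated at Screening, Baseline, the last day of the dose adjustment and PD Phases", plus the follow-up clinic visits. The same section attaches actions to the result. An unexpected fall below 50,000/mm³ leads to HIT antibody testing, and a positive antibody to discontinuation. An expected fall, such as one from chemotherapy, leads to a temporary stop of dalteparin.

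Section 9.1.8 places the platelet count in the Hematology/Coagulation panel ("Total White Blood Cell Count with differential, Platelet Count, PT, aPTT") and assigns the work to the site: "The safety lab tests below will be conducted at the institutional local lab".

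Table 1 has a row for "Hematology/Coagulation" and, directly below it, one for "Antithrombin Activity". At Visit 3 (Dose Adjustment) the second is marked and the first is not.

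The visit lists follow Table 1. Section 9.3.2 includes "Antithrombin level (once at the end of the Dose Adjustment Phase") along with anti-Xa and anti-IIa, but no hematology. Section 9.3.3, for the PD Phase, does include it: "Clinical Laboratory (hematology/coagulation/clinical chemistry at the end of this phase").

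**The concern.** Coordinators usually work from the flowchart and the visit list. Here both leave out a safety count that the thrombocytopenia section asks for, in a trial of a heparin. The HIT test and the dosing hold can only start once someone has a platelet count, so a missing scheduled count means a fall may be found later.

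The eligibility rules in Section 6.3 make the early window relevant. Exclusion applies only at 50,000/mm³ or below, so a child may enter just above the action threshold. Up to 4 days of therapeutic heparin or LMWH for the qualifying clot is allowed before entry, so heparin exposure may predate Day 1. The study has no data monitoring committee (Section 13), so detection rests mainly with the sites.

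**Working it through.** The plan gives no figure to reproduce. The check is a comparison of the three places, followed by simple day counting.

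**Side by side**

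| Time point | Section 7.1.1: platelets | Table 1: Hematology/Coagulation | Table 1: Antithrombin | Visit list in Section 9.3: hematology |
|---|---|---|---|---|
| Screening / Baseline | yes | marked | marked | yes (9.3.1) |
| Visit 3, Dose Adjustment | yes, last day | **blank** | marked | **no** (9.3.2) |
| Visit 4, PD | yes, last day | marked | marked | yes, end of phase (9.3.3) |
| Visits 5, 6, 7 | yes | marked | marked | yes (9.3.4, 9.3.5) |

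The antithrombin row lines up with the hematology row column by column and is marked at Visit 3, so the blank is not a shifted or lost cell. Section 9.3.2 repeats the omission in prose. No Table 1 footnote adds a count at Visit 3. Footnote 5 only says what to do once a count is below 50,000/mm³.

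**Delay of the first scheduled on-treatment count (children who enter the PD Phase)**

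Inputs:
- Dose Adjustment ends on day *D*, from 1 to 7 (Table 1).
- The PD Phase lasts *L* days, from 1 to 7 (Section 5.2: "The PD Phase will last for 1 to 7 days in order to complete two PD samples for each subject").
- Assumption: the PD Phase starts the day after Dose Adjustment ends.

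Results:
- First count under Section 7.1.1: day *D*, so Day 7 at the latest.
- First count under Table 1 and Section 9.3.3: day *D* + *L*, so 7 + 7 = Day 14 at the latest.
- Delay: (*D* + *L*) − *D* = *L*, that is 1 to 7 days.

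**Time since the last pre-dose count**

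Footnote 3 of Table 1 lets the pre-dose laboratory work be done once if Screening falls within 48 hours of Baseline. The last pre-dose count is then 0 to 2 days before Day 1.
- Section 7.1.1: from (1 − 1) + 0 = 0 days to (7 − 1) + 2 = 8 days.
- Table 1: from (2 − 1) + 0 = 1 day to (14 − 1) + 2 = 15 days.

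The 15 days needs the earliest permitted pre-dose count and both phases at full length. It is a worst case, not a typical value.

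**Children who do not enter the PD Phase**

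A child who misses the target range by Day 7 is withdrawn. Section 6.3.1.1 then asks, if possible, for all the Visit 7 assessments, and Section 9.3.5 includes hematology among them. The delay above does not apply to these children.

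**Why there is no fixed share of missing counts**

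A child treated through Visit 7 has 5 on-treatment counts under Section 7.1.1 (end of Dose Adjustment, end of PD, Visits 5, 6 and 7) and 4 under Table 1. A non-cancer child may stop 6 weeks (42 days) after the PD Phase, which is between Day 2 + 42 = 44 and Day 14 + 42 = 56. Visit 7 (Days 75–104) is then off treatment and Visit 6 (Days 45–74) may be. The count under Section 7.1.1 is then 3 or 4 rather than 5.

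**The case against.** The best defence is grammatical. Section 7.1.1 uses the singular for the day, so the phrase could mean one day that closes the two phases together. On that reading it agrees with Table 1 and Sections 9.3.2 and 9.3.3, and nothing is missing. This reading is possible but weaker. The two phases are separate visits with separate ends. Footnote 3 of Table 1 uses a parallel construction for antithrombin, evaluated only once during the two phases, and Sections 9.3.2 and 9.3.3 carry that out once at the end of each. At best the wording is ambiguous, which a safety rule should not be.

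A second objection is that the effect is limited, and this largely stands. Withdrawn children are covered by the Visit 7 assessments where possible. A bleed or clot prompts an unscheduled event visit at which hematology is listed, although footnote 9 leaves those tests to the investigator's discretion. The number of permitted dose adjustments adds nothing, since the documents do not link it to platelet falls.

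A third objection also stands: no rule in the documents gives Section 7.1.1 precedence over Table 1, and two of the three places agree with each other. Amending Section 7.1.1 would equally remove the conflict.

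A reader might infer that every child loses one in five on-treatment counts (20%). The documents do not support that, because the number of counts depends on treatment duration and on whether the child reaches the PD Phase.

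**Conclusion.** The inconsistency is real on the natural reading of Section 7.1.1. For children who proceed to the PD Phase, following Table 1 and Section 9.3.2 puts the first scheduled on-treatment platelet count about 1 to 7 days later, with Day 14 rather than Day 7 as the latest date. This rests on the phase lengths in the protocol and on the PD Phase starting the day after Dose Adjustment ends.

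The documents do not allow an estimate of how many children would have a platelet fall in that interval. Nor do they support saying that platelets go unmonitored, since discretionary and event-driven tests remain possible. The primary endpoints, the sample size and the censoring rule are untouched. The point is worth correcting, at modest severity, as an internal inconsistency in a safety schedule and not as a matter of design preference.

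**What to change.** In Table 1, add a Hematology/Coagulation mark at Visit 3, with a note that at least a platelet count is needed, once, on the last day of the phase. In Section 9.3.2, add a matching bullet. In Section 7.1.1, saying the last day of each phase would remove the second reading.

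The cost is one table cell, one bullet and one local-laboratory count per child. The count can be drawn with the end-of-phase antithrombin sample, also a local test. The extra blood volume should be small, but the documents do not state it, and it matters most in the youngest children, who are eligible from just above 3 kg.

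If the sponsor did not intend a count at this point, it should amend Section 7.1.1 instead and accept the later first count. Either way, the three places should agree. The HIT rule and the stopping criterion for unexpected thrombocytopenia need no change.
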